In the initial contact with an applicant, a brief screening interview will be conducted to inform interested persons about the study and to confirm that the person might qualify for the study. This interview may take place over the phone or in person when an applicant initially inquires about the study. Prior to asking any questions, the interviewees will be told that they do not have to answer any of the questions and can stop the interview at any time. In cases where the brief screening interview is conducted in-person (i.e., at an inpatient treatment program or at the Therapeutic Workplace), the interview will take place in a private area to ensure confidentiality. If the results of the brief screening interview suggest that the applicant might be eligible, the applicant will be invited to sign the study consent form to be screened more fully for study eligibility. Results of the brief screening interviews will be entered into a database, but no identifying information will be entered in this database. A person's name, phone number and address will only be written on the brief screening interview form if the person is invited to participate in an Initial Screening Interview. This contact information will be used to help schedule the interview and to allow us to reschedule the interview as needed. If a person decides not to participate in the Initial Screening Interview, his/her brief screening interview will be shredded. Hard copies of the brief screening interview forms will only be saved for participants who signed the Initial Screening Consent form.

Initial Screening Interview

Initial screenings will occur at the collaborating program or at our research unit to determine eligibility for the study and collect baseline data on the study population. The participant will be asked to sign a consent form to allow his/her medical clinic to release medical records to determine study eligibility, to characterize medications used, and to characterize the population. The Initial Screening Interview will take place in a private area to ensure confidentiality. Participants will be paid for completing the screening interview. Patients who meet criteria for inclusion in the study will be invited to participate in the main randomized controlled study.

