Reloadable credit card. At the start of each participant's enrollment, each participant will be given a reloadable credit card. When the participant calls to get the results of a given viral load test, the Incentive staff will tell the participant the results. If the participant met the criterion for the incentive, the Incentive staff will tell the participant the amount of the incentive earned and add the incentive amount to the participant's reloadable credit card. This procedure will ensure that participants monitor the results of their viral load testing and know when, why and how much is added to their credit card. That card can then be used as a regular credit card to make purchases at most businesses. We currently use this reloadable credit card system in our Therapeutic Workplace incentive program, and it has proved very efficient and highly acceptable to participants.

Usual Care Control Group

Usual Care Control Only participants will receive the standard HIV medical care described above offered in their medical clinic. Participants in this group will not receive added viral load testing, feedback or incentives, beyond the viral load testing conducted as a routine part of their medical care.

Assessments

For all participants, assessments will be conducted at intake to determine eligibility and characterize participants. Outcome assessments will be conducted at intake, every 3 months throughout the 2-year intervention evaluation and every 6 months of the 1-year follow-up period. Except for the computerized delay discounting task, the assessments will be administered using the Qualtrics web-based software (<http://qualtrics.com/>) to administer and record responses for the questionnaires administered under this protocol. When necessary (e.g., if the web server is not operational), a printed version of the questions will be used.

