visual analog scale (VAS) to assess ART adherence in which participants mark a 100 mm line to indicate their percent adherence to their antiretroviral medications over the previous 4 weeks (Buscher et al., 2011; Walsh et al., 2002). Responses on this VAS have been associated with pill taking with MEMS (Buscher et al., 2011; Walsh et al., 2002), pill count (Walsh et al., 2002), and pharmacy records (Buscher et al., 2011). 7) Assess whether each participant refilled their ART prescription for each month, the pharmacy that filled each prescription, and the medication. 8) Pharmacy records will be obtained (with participant permission) to confirm self-reported data. 9) Participants will be asked how many primary HIV care visits they had in the past 3 months using procedures and definitions used in a prior multisite study (Purcell et al., 2007). Medical records will be obtained with permission to confirm self-reports. 10) The *Modified Economic Form 90 AIR/ED* will be created for this study based on the Economic Form 90 AIR/ED (Bray et al., 2007; Miller and Del Boca, 1994; Scheurich et al., 2005; Tonigan et al., 1997) to collect patient data on all health care utilization within the past 180 days. 10) A Modified SASCAP (Zarkin, Dunlap et al. 2004) will be used to estimate the costs associated with services in the study conditions. The SASCAP (www.rti.org/sascap) assesses activity-level resource use and cost data for intervention staff, consultants, and non-labor resources (e.g., building space) used in the provision of intervention services. The SASCAP method reliably estimates the costs of intervention activities and the cost per participant. Zarkin and Dunlap have applied this micro-costing approach (Zarkin et al., 2003, 2005, 2008, 2010; Dunlap et al., 2010). 11) A multiple-choice test evaluating the HIV Education Course.

b. Study duration and number of study visits required of research participants.

Participants in the incentive group will receive the incentive intervention for two years. For all participants, assessments will be conducted at intake to determine eligibility and characterize participants. Outcome assessments will be conducted at intake, every 3 months throughout the 2-year intervention evaluation and every 6 months of the 1-year follow-up period.

c. Blinding, including justification for blinding or not blinding the trial, if applicable.

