Specific Aim. Assess the effectiveness of the incentive intervention for decreased or undetectable viral loads in promoting retention in HIV medical care. We will assess whether the participant attended at least 2 medical visits per year (Mugavaro et al. 2012; Y/N each year based on self-report and medical records).

Specific Aim. Assess the effectiveness of an empirically-based incentive intervention in promoting undetectable levels of viral loads, maintenance of antiretroviral prescriptions, consistent adherence to antiretroviral therapy, and retention in HIV care after the incentive intervention is discontinued. We will assess measures described above but at the two 6-month assessments during the year after the intervention ends.

Moderator Analysis Measures

Specific Aim. Determine if drug (cocaine or opiate) dependence, alcohol dependence, depression, health literacy, and impulsivity assessed at intake moderate viral load suppression and response to the incentive intervention. A dichotomous value (Y/N) for cocaine, opiate and alcohol dependence will be used as assessed by the CIDI. The total score on the TOFHLA will be used to assess health literacy. The total score on the Beck Depression Inventory will be used to assess depression. Log transformed k for each participant on the delay discounting task will be used to assess impulsivity.

Mediator Analysis Measures

Specific Aim. Determine if antiretroviral medication adherence as assessed by qualitative HRMS blood tests of 15 antiretroviral medications mediates the effect of the incentive intervention on viral load suppression. We will assess mediating effects of medication adherence as assessed by qualitative blood testing on viral load using the method of Baron and Kenny (1986) as described below.

Economic Outcome Measures

Specific Aim. Assess the costs of HIV medical care for Usual Care and Incentive groups. We will assess the total cost per participant of both study interventions including cost of the incentive program (see below). We expect that Incentive group costs will be higher relative to the Usual Care due to the incentive program and because we expect that the Incentive participants will have greater treatment engagement.

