Primary outcome analyses. We will fit a longitudinal logistic regression model $\text{logit}(Y_{ij}) = \beta_0 + \beta_1 tx + \beta_{2-6}x_{2-6} + \epsilon_{ij}$, where Y_{ij} is the presence of a detectable viral load for the i th person at the j th timepoint (8 visits over two years of treatment), β_1 is the covariate of interest representing the expected decrease in log odds of a detectable viral load as a function of assignment to the treatment group, and β_{2-6} are the coefficients for the 5 randomization covariates. Additional models with time and time by treatment interactions will be fit secondarily to assess time trends in treatment effect.

Secondary outcome analyses. We will fit analogous longitudinal logistic regression models for HRMS-verified ART adherence, self-reported adherence, prescription maintenance, and attendance at HIV medical care visits. We will assess post-treatment effects by fitting analogous models for each outcome, but using only data from the two post-treatment visits.

Moderator analyses. For the primary outcome, we will fit models with interactions between treatment and each of the 5 randomization covariates (drug dependence, alcohol dependence, TOFHLA total score, delay discounting, and Beck Depression score) to assess whether treatment effect varies as a function of the putative moderator. For example, for CIDI drug dependence, we would fit the model $\text{logit}(Y_{ij}) = \beta_0 + \beta_1 tx + \beta_{2-6}x_{2-6} + \beta_7 tx * \text{drug dependence} + \epsilon_{ij}$, where β_1 would represent the treatment effect (expressed as a difference in log odds of a detectable viral load between treatment and control groups) among individuals without drug dependence, and β_7 would represent the difference in treatment effect between individuals with and without drug dependence. All moderator analyses will be considered exploratory and will not be corrected for multiple comparisons. These variables will be examined as potential moderators because drug use (Mimiaga et al., 2013), health literacy (Kalichman et al., 2008),

and depression (Murphy et al. 2013) has each been associated with poor adherence to antiretroviral medications. Impulsivity will be assessed as a potential moderator because high levels of impulsivity have been associated with poor health decision making and adverse health behaviors (Axon et al., 2009; Bickel et al. 2014; Bradford et al., 2010).

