Mediation analysis. We will assess potential mediating effects of medication adherence as assessed by qualitative blood testing on viral load using the method of Baron and Kenny (1986). Specifically, this involves estimation of (1) the effect of treatment assignment (incentives) on undetectable viral load without controlling for medication adherence, (2) the direct effect of incentives on medication adherence, and if these two steps yield clinically and statistically significant effects, 3) the effect of incentives on viral load after controlling for medication adherence ($\text{logit } (Y_{ij}) = \beta_0 + \beta_1 x_i + \beta_{2-6} x_{2-6} + \beta_7 \text{adherence} + \epsilon_{ij}$). If medication adherence does mediate the effect of the incentives on presence of a detectable viral load, in this final model we would expect the effect of treatment (β_1) to be attenuated relative to the step 1 model, and for adherence (β_7) to be a clinically and statistically significant predictor of presence of a detectable viral load.

Missing data. We expect to collect $\geq 80\%$ of 3-month assessments (see below). Our primary approach will be to impute all missing values as the adverse outcome (e.g., detectable viral load). Model parameter estimates from this approach will be compared to a method without imputation. If these methods yield differing results, conclusions will need to be tentative. To investigate sensitivity to missing values, participants with and without missing values will be compared by covariates and treatment assignment.

ECONOMIC ANALYSES

We will use the provider perspective using a modified SASCAP and the research team's financial records. Intervention activities will be captured with the modified Economic Form 90 AIR/ED.

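### The HIV-care-visit question looks back 3 months at post-treatment assessments held 6 months apart, so it covers half of the year on which post-treatment retention is scored

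*Combined protocol and SAP*

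**What the plan says.** Item 9 of the assessment list in Section 4a states: "Participants will be asked how many primary HIV care visits they had in the past 3 months". The list is headed for intake, 3-month and 6-month follow-up assessments and says its items may be used at all of them. It gives no other look-back for the 6-month assessments. Assessments take place "every 3 months throughout the 2-year intervention evaluation and every 6 months of the 1-year follow-up period".

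Section 7a defines retention as two or more medical visits in a year, scored "Y/N each year based on self-report and medical records". For the period after the incentives stop, it says: "We will assess measures described above but at the two 6-month assessments during the year after the intervention ends". Retention is one of the measures named there. Section 7b (Secondary outcome analyses) fits the post-treatment models "using only data from the two post-treatment visits".

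On the second source, item 9 adds: "Medical records will be obtained with permission to confirm self-reports". The modified Economic Form 90, on the same list, asks about all health care use over 180 days, but Section 7b assigns it to the economic analyses.

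**The concern.** A yearly visit count needs a look-back as long as the gap between assessments. During treatment the two match. After treatment they do not: the first three months of each six-month interval fall outside the question. The same two-visit rule is therefore applied to almost complete self-report in the treatment years and to about half in the follow-up year.

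The error would be hard to see in the data. A participant who answers the question has a recorded value; it is merely too low. The plan's main missing-data rule, to "impute all missing values as the adverse outcome", acts only on absent values, and so does its comparison with an analysis without imputation.

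At stake is one secondary outcome in the follow-up year. It bears on a stated objective, whether effects last after the intervention is discontinued, because a loss of visit capture can look like a loss of retention.

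**Working it through.** **Plan's own schedule.** 24 / 3 = 8 treatment assessments and 12 / 6 = 2 post-treatment assessments (months 30 and 36), as the plan states.

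**Coverage of the 3-month question**, taking 3 months as 91 days:
- Treatment: 8 × 91 = 728 of 730 days.
- Post-treatment: 2 × 91 = 182 of 365 days. Months 1–3 and 7–9 are not asked about.
- For comparison, the 180-day form: 2 × 180 = 360 of 365 days.

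**Participants who meet the two-visit rule but would be scored as not retained on this question alone**, both interviews completed. The documents give no visit patterns, so two are assumed.
- *Random timing.* With k visits and p = 182/365 = 0.499, P(fewer than 2 captured) = (1 − p)^k + k·p·(1 − p)^(k − 1). For k = 2, 3, 4 this is 0.751, 0.502, 0.315. For k = 6, with p = 0.5, it is 1 − 0.891 = 0.109.
- *Even spacing, random start.* At 6-month spacing both visits fall inside the windows or both fall outside: 0.504 missed. At 4-month spacing: 0.504. At 3-month spacing one visit falls in nearly every quarter: 0.006.

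**Allowing for records.** Let m be the share of participants with no usable records. The documents give no figure; 10% to 30% is an assumption. Misclassified share of truly retained participants = m × share missed:
- Random timing: 0.10 × 0.315 = 3.1% to 0.30 × 0.751 = 22.5%.
- Even spacing: 0.10 × 0.006 = 0.1% to 0.30 × 0.504 = 15.1%.
- With complete records (m = 0): none.

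**Effect on the comparison between arms.** With true retention R and capture probability s, observed retention = R × [(1 − m) + m × s]. Take m equal in both arms.
- *Same visit count in both arms.* Both are multiplied by the same factor. With m = 20% and s = 0.25 (2 random visits) it is 0.80 + 0.20 × 0.25 = 0.85, so a true difference in percentage points shrinks by 15%.
- *Different visit counts.* Let R = 80% in both arms, with 2 visits in control (s = 0.25) and 4 in incentive (s = 0.6875), random timing, p = 0.5. At m = 20%: control 0.80 × 0.85 = 68.0%; incentive 0.80 × (0.80 + 0.20 × 0.6875) = 75.0%. That is a false 7-point benefit. At m = 10% it is 77.5 − 74.0 = 3.5 points; at m = 30%, 72.5 − 62.0 = 10.5 points. If the visit counts were reversed, so would be the sign.

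**Effect on change over time.** Suppose visits follow a Poisson distribution with mean 4 a year throughout (assumption). Full coverage gives P(at least 2) = 1 − 5e^(−4) = 90.8%; half coverage gives 1 − 3e^(−2) = 59.4%. On this question alone retention would appear to fall 31.4 points with no change in behaviour. If 20% rest on it alone, the apparent fall is 0.20 × 31.4 = 6.3 points.

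**The case against.** The strongest reply is that retention does not rest on self-report alone. Section 7a names medical records as a co-source, and complete records reduce the error to zero. This stands, and it is the main reason why the point is minor. It does not dispose of it: item 9 obtains records with permission and to confirm what participants report, and confirming a 3-month answer does not require a search of the months that were not asked about. No rule says which source prevails, and no search over the whole post-treatment year is specified.

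A second reply is that visits may be regular. Section 4a gives 12 weeks as the standard interval for viral load testing. If HIV care visits follow that rhythm, about four evenly spaced visits a year, the loss is about 1% even without records. This also stands; the larger figures need fewer or irregular visits. Partial records would lower them further.

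Some stronger readings are tempting but unsupported:
- *All self-report covers only half the year.* The 180-day form is also self-report and covers 360 of 365 days. The shortfall belongs to this question. Equally, the plan neither links the form to retention nor says that it identifies primary HIV care visits.
- *The phrase "using only data from the two post-treatment visits" excludes records.* In context it separates post-treatment data from the eight treatment assessments and does not bar records obtained for those visits.
- *The screening release, given "to determine study eligibility, to characterize medications used, and to characterize the population", does not extend to retention.* That sentence describes screening. Item 9, the Risks section and the COVID-19 procedures all foresee records or clinic results during follow-up, and the consent pages are not in the reviewed copy.
- *With equally complete records the error only dilutes the difference.* The working shows otherwise, because capture depends on visit count.

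**Conclusion.** The mismatch is real and follows from the plan's own schedule: 182 of 365 post-treatment days against 728 of 730 treatment days for the same question and the same two-visit rule. The coverage figures rest on no assumption beyond a 91-day quarter.

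The consequence is conditional. It affects only participants whose records are not usable. For them, between about 1% (four evenly spaced visits) and 75% (two randomly timed visits) of truly retained participants with 2 to 4 visits would be scored as not retained on this question alone. The share without records and the visit patterns are assumptions, so neither the size nor the direction of any bias in the odds ratio can be derived from the documents. A fall in retention after treatment could be partly an artefact.

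Severity is minor. One secondary outcome in the follow-up year is affected, and the primary viral-load outcome is not.

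**What to change.** At months 30 and 36, ask about HIV care visits in the past 6 months (2 × 6 = 12 of 12 months) and keep the 3-month wording at the 3-month assessments. State that visits in medical records are counted over the whole post-treatment year as a source in their own right, with the 180-day form as a supplement where it identifies HIV care visits. Report by arm how many participants' retention status rests on self-report alone.

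The cost is one re-worded question at two assessments and a records search over a defined year, with no added visits. The downside is longer recall, 6 months instead of 3. The new wording can be used in the interviews still to be held by telephone. For post-treatment interviews already done, only the records and the 180-day form can help.

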During the research interviews, participants will be asked to complete a contact information sheet. The contact information sheet will include the participant's contact information as well as the contact information of family members or other individuals we may contact by phone or in writing in order to locate the participant for future research interviews. Participants who do not qualify for the study will be referred to services that they need or want. We have used similar recruitment procedures in prior studies (e.g.,

Donlin et al., 2008; [name] et al., 2007). See the Letters of Support section for letters from the Medical Directors of these clinics.

Standard HIV Medical Care

Upon enrollment, participants will be taught about the benefits of HIV medical care, ART adherence and the need to maintain nearly perfect adherence. Participants will be able to earn incentives for engaging in this education. Participants will be able to earn up to about \$100 for completing the program. Some or all of the training may be given through a computer-based training program. We may also evaluate the effectiveness of the education program by giving participants tests before and after participants complete parts or all of the training program. We may re-administer the test at the end of the intervention to measure retention.

If a participant is not currently receiving HIV medical care, the participant will be referred to an HIV medical care clinic. Participants will typically receive their HIV medical care at the Comprehensive Care Practice or the Chase Brexton Health Services clinic.

Experimental Design

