Participants (N = 200) who complete the HIV Medical Care Education program will be randomly assigned to a Usual Care Control group or the Incentive group. A computerized urn randomization procedure (Wei & Lachin, 1988) will be used to balance groups on five baseline characteristics that may influence outcome: (1) opiate or cocaine positive urine sample at intake to the study (Y/N); (2) Self-reported use alcohol to intoxication on 20 or more days in the past 30 on the ASI (Y/N); (3) health literacy as assessed on the TOFHLA (score \leq the rolling median, Y/N); (4) impulsivity as assessed by delay discounting (k value from the raw discounting data for each participant, which is an index of impulsivity (\leq the rolling median of k, Y/N); and (5) depression as assessed by the Beck Depression Inventory (score \leq the rolling median, Y/N). Participants will be stratified by DSM V cocaine, opiate and alcohol dependence, health literacy, and depression at intake because drug use (Mimiaga et al., 2013), health literacy (Kalichman et al., 2008), and depression (Murphy et al. 2013) has each been associated with poor ART adherence. Participants will be stratified based on measures of impulsivity because high levels of impulsivity have been associated with poor health decision making and adverse health behaviors (Axon et al. 2009; Bickel et al. 2014; Bradford et al., 2010). Participants will be taught the details of their group with written instructions and quizzes. Participants will earn up to about \$15 for answering questions on the quiz.

Incentive Group

The Incentive group will receive the novel empirically-based incentive intervention to promote long term suppression of HIV-1 RNA (viral load) being evaluated in this study. The incentive intervention will employ features and parameters that have been shown critically important to promote therapeutic behavior change in drug users and other populations (Higgins et al., 2008; Lussier et al., 2006; [name] et al., 2011). Participants will be taught the details of the incentive program with written instructions and quizzes.

A Prescription for ART. When a participant gets assigned to the Incentive group, he/she will be asked if he/she has a current prescription for ART and if he/she has at least a 2-day supply of medication. As described below, blood draws and the incentive program described below will not begin until the participant has an active ART prescription and has at least a 2-day supply of medication.

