Participants will not be blinded as to their study condition because participants in the incentive intervention cannot be blind to that intervention.

d. Justification of why participants will not receive routine care or will have current therapy stopped.

All participants will receive the best HIV medical and appropriate referrals to other care that is available in their respective HIV medical clinics. Participation in this study will not limit their access to the highest quality medical care that is available in their medical clinics.

e. Justification for inclusion of a placebo or non-treatment group.

There is not a placebo or non-treatment group in this study.

f. Definition of treatment failure or participant removal criteria.

Participants will be removed from the study if they threaten the safety of the research staff or other research participants.

g. Description of what happens to participants receiving therapy when study ends or if a participant's participation in the study ends prematurely.

Participants will continue to receive HIV medical care as long as that care is available in the medical clinic that they attend.

5. Inclusion/Exclusion Criteria

Applicants will be accepted if they: a) are ≥ 18 yrs old; b) have been diagnosed with HIV for at least 12 weeks; c) have a detectable viral load (>200 copies/mL); and d) are not currently receiving HIV medical care or have been in HIV medical care for at least 12 weeks. Applicants will be ineligible if they a) report current suicidal or homicidal ideation; or b) have a severe psychiatric disorder.

6. Drugs/ Substances/ Devices

NA

a. The rationale for choosing the drug and dose or for choosing the device to be used.

NA

b. Justification and safety information if FDA approved drugs will be administered for non-FDA approved indications or if doses or routes of administration or participant populations are changed.

NA

c. Justification and safety information if non-FDA approved drugs without an IND will be administered.

Date: July 28, 2014

Principal Investigator: [name]

Application Number: IRB00044740

7. Study Statistics

We will compare the Incentive and Usual Care Control groups on primary, secondary and economic measures. To preserve statistical power and minimize the likelihood of false conclusions, we identified one primary biological outcome measure and a limited number of secondary and economic measures. Each measure is associated with a *Specific Aim*.

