Specific Aim. Assess the cost-effectiveness of the empirically-based incentive intervention for undetectable viral loads. We will assess incremental cost-effectiveness ratio (ICER) by dividing the difference in costs of two interventions by the difference in effects of the two interventions during the 2-year intervention evaluation period on viral load suppression (see below). The ICER can be interpreted as dollars spent per unit of desired outcomes gained. The Incentive Intervention should yield a better ICER.

Specific Aim. Assess the cost-benefit of empirically-based incentive intervention for undetectable viral loads. We will perform a Cost-Benefit Analysis (CBA) to examine the monetized benefits relative to costs for the Usual Care Control and Incentive intervention conditions. The economic outcomes are health care utilization during the 2-year intervention evaluation period (see below). We expect that the Incentive Intervention will yield greater economic benefits relative to its costs than the Usual Care Control.

Measures assessed repeatedly over time will be analyzed with a longitudinal logistic regression model. Within-person correlated outcomes will be handled using generalized estimating equations (GEE; Zeger, Liang, & Albert, 1988). Measures assessed once will be analyzed using logistic regression. The magnitude of effects will be expressed using odds ratios with 95% CI. Intent-to-treat analyses will be adjusted for covariates used for stratification (Pocock et al., 2002). Two-sided tests with p-values <.05 will be considered significant.

- b. Statistical plan including sample size justification and interim data analysis.

STATISTICAL ANALYSES

Measures assessed repeatedly over time will be analyzed with a longitudinal logistic regression model. Within-person correlated outcomes will be handled using generalized estimating equations (GEE; Zeger, Liang, & Albert, 1988). Measures assessed once will be analyzed using logistic regression. The magnitude of effects will be expressed using odds ratios with 95% CI. Intent-to-treat analyses will be adjusted for covariates used for stratification (Pocock et al., 2002). Two-sided tests with p-values <.05 will be considered significant.

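### HIV care status at entry, which eligibility criterion d records for every participant, is not a covariate in the outcome models; adding it is a low-cost efficiency gain, not a correction of bias

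*Combined protocol and SAP*

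**What the plan says.** Section 5 (Inclusion/Exclusion Criteria) accepts people who "have a detectable viral load (>200 copies/mL") and who meet criterion d: "d) are not currently receiving HIV medical care or have been in HIV medical care for at least 12 weeks". Under Standard HIV Medical Care (Section 4a), "If a participant is not currently receiving HIV medical care, the participant will be referred to an HIV medical care clinic".

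Under Experimental Design (Section 4a), an urn procedure "will be used to balance groups on five baseline characteristics that may influence outcome". The five are drug-positive urine, drinking to intoxication, health literacy, delay discounting and depression score. Section 7 states that "Intent-to-treat analyses will be adjusted for covariates used for stratification", and in the primary model the terms after treatment "are the coefficients for the 5 randomization covariates". The secondary outcomes use analogous models. The exploratory moderators are the same five constructs. Care status at entry is in none of these lists.

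In the Incentive arm, "blood draws and the incentive program described below will not begin until the participant has an active ART prescription" and at least a 2-day supply of medication.

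**The concern.** Criterion d joins two groups that stand at different points on the care pathway set out in the Background (linkage, retention, ART, suppression). One still has to be linked to care. The other has been in care for at least 12 weeks without being suppressed. Section 7 itself names adherence to ART and staying in care as conditions for an undetectable viral load, and the urn factors were chosen because they may influence outcome. By that reasoning care status is a natural candidate covariate. The case is strongest for the secondary outcomes of retention in care and prescription refills, because care status at entry is close to a baseline value of the retention outcome.

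If care status predicts outcome beyond the five listed covariates, leaving it out costs some power. The Power Analysis describes the adjusted sample of 160 as only slightly above the largest number required, so cheap efficiency is useful.

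**Working it through.** **Inputs from the plan (Section 7).** 200 randomised; 160 after 20% missing; eight assessments; 15-point difference; two-sided 0.05; 80% power.

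**Assumptions.** 1:1 allocation (the ratio is not stated). Out-of-care share f = 10-50%. Difference in suppression between the two care groups D = 0-30 points. The text does not give the within-person correlation ρ, and the control rates stand only in a figure that is not reproduced.

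**1. The plan's own figure.** 200 × 0.80 = 160 reproduces. For the required N, the exchangeable binary formula is

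N = 2(z_α + z_β)² [p₁q₁ + p₂q₂] (1 + 7ρ) / (8d²).

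At the worst-case rates of 42.5% and 57.5%, with (1.960 + 0.842)² = 7.849:

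N = 2 × 7.849 × 0.48875 / (8 × 0.0225) × (1 + 7ρ) = 42.6 × (1 + 7ρ).

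This gives 132, 162, 192 and 222 at ρ = 0.30, 0.40, 0.50 and 0.60. The stated 160 matches ρ of about 0.39. With ρ unknown, the power statement can be neither confirmed nor refuted; ρ = 0.39 serves below as the value at which 160 gives 80%.

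**2. Chance imbalance at 100 per arm.** SD = √(2f(1−f)/100). At f = 30% this is √0.0042 = 6.5 points, a 95% range of ±12.7. At f = 15% and 50% the ranges are ±9.9 and ±13.9. At f = 30%, an imbalance of 10 points or more has probability 0.12 (z = 10/6.48 = 1.54).

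The shift in the treatment difference is imbalance × D. At f = 30% and D = 20, the 95% range is 12.7 × 0.20 = ±2.5 points, and a 1-SD imbalance gives 6.5 × 0.20 = 1.3 points. Over f = 10-50% and D = 10-30, the 95% shift runs from ±0.8 to ±4.2 points, against a 15-point target.

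**3. Share of variance that adjustment removes.** R² = f(1−f)D² / [p(1−p)(1+7ρ)/8]. At f = 30%, D = 20, p = 0.5 and ρ = 0.39: 0.21 × 0.04 / 0.117 = 7.2%. This is also the share of the sampling variance of the treatment difference that comes from chance imbalance in care status, so steps 2 and 3 describe one cost, not two. Power becomes Φ(2.80/√(1−0.072) − 1.96) = 82.8%.

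| f | D (points) | R² | Power by formula, from 80.0% | Simulated power, without → with covariate |
|---|---|---|---|---|
| 10% | 10 | 0.8% | 80.3% | 76.8 → 76.6% |
| 10% | 20 | 3.1% | 81.2% | 77.0 → 78.0% |
| 10% | 30 | 6.9% | 82.7% | 74.8 → 76.9% |
| 30% | 10 | 1.8% | 80.7% | 76.9 → 77.9% |
| 30% | 20 | 7.2% | 82.8% | 75.8 → 79.0% |
| 30% | 30 | 16.1% | 86.4% | 74.9 → 81.2% |
| 50% | 10 | 2.1% | 80.8% | 77.2 → 77.9% |
| 50% | 20 | 8.5% | 83.4% | 75.8 → 78.8% |
| 50% | 30 | 19.2% | 87.6% | 73.4 → 80.5% |

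The simulation used beta-binomial counts, N = 160 and ρ = 0.43. At D = 0, power did not improve.

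A second simulation used a logistic model with robust variance, N = 200 and ρ = 0.5. Power went from 0.80 to 0.82 (D = 20, f = 30%), from 0.81 to 0.85 (D = 30, f = 30%) and from 0.78 to 0.84 (D = 30, f = 50%). It stayed at 0.81 with no difference.

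**4. Validity.** In the first simulation the unadjusted estimate averaged 14.8 to 15.1 points against a true 15. Type I error was about 5-6% with or without the covariate.

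**5. What an interaction test could detect.** With f = 30% (30 and 70 per arm), ρ = 0.5 and p = 0.5, the variance per person is 0.25 × 4.5/8 = 0.1406. The out-of-care subgroup effect has SE √(2 × 0.1406/30) = 9.7 points, a 95% half-width of about 19. The interaction has SE √(2 × 0.1406/30 + 2 × 0.1406/70) = 11.6 points, so 80% power needs 2.80 × 11.6 = about 32 points.

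**The case against.** Adjusting for the randomisation factors is a coherent, prespecified choice, and a sixth covariate is optional. That stands, and it sets the priority.

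The size of the gain is also open. The in-care group is selected for still being viremic after at least 12 weeks of care, so it may do no better than people who are newly linked; the difference could be small or reversed. The sentence in Section 7 about staying in care concerns follow-up, not status at entry. The calculations take care status alone. The plan says that drug use, health literacy and depression are associated with poor adherence, so overlap with those covariates would shrink the gain. All of this stands.

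A reader might go further than the documents allow in three ways:

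- **That imbalance biases the primary odds ratio or inflates type I error.** Under randomisation it is ordinary sampling error, already inside the interval.
- **That the out-of-care group in the Incentive arm starts late or never.** The gate is a prescription and a 2-day supply, not care status. Criterion d does not require people in care to be on ART, and someone out of care may still hold a prescription. A different effect by care status is plausible, but late starting is not documented.
- **That the trial must separate the two groups because it aims at use in HIV clinics.** Section 8 speaks of wide use in adults living with HIV, and recruitment extends beyond clinics.

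**Conclusion.** The point holds as an efficiency suggestion of low priority. A plausible baseline predictor, known for everyone before randomisation because eligibility depends on it, is left out of the outcome models.

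Over out-of-care shares of 10-50%, and on the simulated comparison at N = 160, adjustment gains about 0-3 points of power for a 10-20 point difference in suppression, about 2-7 points for a 30-point difference, and nothing if there is no difference. These figures rest on an assumed share, difference and within-person correlation, and on no overlap with the five existing covariates. In the planned logistic model the gain shows as power, not necessarily as a smaller standard error of the log odds ratio.

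A reader might infer that adding care status as a moderator would show which group the effect comes from. It would not, unless the two effects differed by about 32 points.

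**What to change.** Before outcome data are analysed, add to the primary and analogous secondary GEE models in Section 7: in HIV care at entry (Y/N, by the branch of criterion d met). If the primary model is already locked, make this a prespecified sensitivity model instead. Report care status at entry by arm in either case. Settling this in advance matters because participants are not blinded, and a covariate added after results are seen would look chosen by the data.

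A treatment by care status interaction may join the exploratory moderators, with a note that its power is low.

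A sixth urn factor is probably no longer possible: the COVID-19 Procedures speak of completing the remaining assessments, which suggests that enrolment has ended.

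The cost is SAP wording, one degree of freedom, and a conditional odds ratio that is defined slightly differently from the one now planned. No new data are needed. The eligibility check establishes the variable, and recent HIV care visits are also asked about and checked against medical records (Section 4a, Assessments).
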